12.5 Power and Sample Size Considerations

Due to correlation among multiple measurements made on the same participants, the information provided by additional tooth sites within an individual is less than that provided by the initial site. For the purposes of power analysis, this may be represented by a variance inflation factor (VIF), which depends on the number of observations per cluster (individual in this case) and the intraclass correlation (ICC). The VIF is calculated as $1 + (\text{average cluster size}) \times \text{ICC}$. The VIF can be used to calculate an effective sample size, which is the number of independent observations that would be required to provide power equal to the larger number of correlated observations that are available to the study.

The actual sample sizes for the analysis of aims other than those based on histology data will not be known in advance, since multiple extractions pr participant will be included in the study. Histology will be conducted on a single site per participant; so variance inflation is not an issue for these measures.

Eighty participants will be recruited, each of which will contribute data on one or more extraction sites. If the average number of extractions per participant is small, say 1.5 or 2, the power of the study will not be severely reduced relative to a study with independent observations, even if the ICC is as large as 0.50. Assuming $\text{ICC} = 0.50$ and an average of 1.5 extractions pr participant, the total number of observations in the study would be 120, $\text{VIF}=1.25$, and the effective sample size would be 96, or an expected effective sample size of 24 extractions in each of the extraction groups. If there were an average of 3 extractions per participant the same assumptions would yield a total sample size of 160 $\text{VIF} = 1.5$, and an effective sample size of 107, or approximately 27 extractions per group.

A conservative approach to power estimation was used, assuming an effective sample size of 25 observations per extraction-implant group. Power calculations utilized the Power and Precision, release 2.00, (Borenstein, 2000) and nQuery Advisor 6.0 (Janet D. Elashoff, 1995-2005) software packages. Power to detect a “medium” effect size, corresponding to a difference between group means equal to 0.50 times the within-group standard deviation (sd) was calculated. Also, the effect size detectable with 80% power was calculated. All power estimates were based on two-sided testing at the 95% confidence level.

The power for SA-1 is largely determined by the size of control group, since the primary comparison is equivalent to a t-test of the mean of the controls vs others. Thus, the assumed effective sample sizes of 25 and 75 would yield approximatey 57% power to detect a medium effect size. The difference detectable with 80% power would be approximately 0.65sd .

Power for SA-2, SA-4 and SA-5 was based on a one-way ANOVA model. The proposed sample size would provide 52% power to detect a medium effect size or 80% power to detect an effect size equivalent to a two-group difference of 0.34sd . These approximations also apply to SA-3, with the appropriate sd being the within-group standard deviation of the changes across the observation times.

The total sample size for SA-5 would be 80, or 20 per group, since this SA is based on histology, with a single extraction per participant. Power to detect a medium effect size would be 42%. The effect size detectable with 80% power is equivalent to a two-group difference of 0.72sd.

Power for SA-6 was based on linear regression with a four-category dummy variable. If stability and group each explain 10% of the observed variance, the proposed sample size would provide 80% power to detect an increment of 8.6% in explained variance for the stability*group interaction.

Power for comparison of rates of infection signs for SA-7 was based on the chi-square test for the odds ratio. The proportions in the two groups were centered on 0.50, in order to provide a conservative estimate of power. The effective sample size of 50 per group would provide 80% power to detect an odds ratio of approximately 3.2 for the association between implant type and infection.

Power estimation for the comparison of bone height measurements (SA-7), for comparison of changes in JEMT index (SA-8) and of changes in crestal bone levels (SA-9) between the two implant types was based on a t-test. The proposed sample size would provide 70% power to detect a medium effect size, and 80% power to detect a difference of 0.565sd between the groups. For SA-8 and SA-9, sd refers to the within-group standard deviation of changes across time.

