This SA will be addressed using mixed-model ANOVA to compare mean bone volume among the four groups. Post-hoc pairwise comparisons will use Tukey's test. The effect of growth factors enrichment will be addressed using contrasts and F-tests to compare the mean of Group-4 with those of each of the other groups. If there is not a significant difference among the group means of Groups 1-3, the combined mean of these three groups will be compared with that of Group-4.

SA-3: Compare soft tissue healing between groups at week-1, week-2, week-4 and after 8 weeks of healing.

The analysis of SA-3 will be mixed-model ANOVA including measurements of healing made at each time points. Time will be included in the model in order to account for unequal spacing of the observational times. The statistical test that will be of primary interest will be the F-test for Group by time interaction.

SA-4: Assess quantitative bone fill across groups after 8 weeks post-extraction healing.

Qualitative bone fill will be compared among four groups using mixed-model ANOVA and the 8 week measurement only. Post-hoc pairwise comparisons will use Tukey's test.

SA-5: Compare qualitative bone fill across groups after 8 weeks post-extraction healing.

Percent new bone, percent residual graft, and percent soft-tissue will be compared among the four groups using ANOVA. For this analysis, there will be a single measurement of each of the variables per participant, so correlated observations will not be an issue in the analysis. Post-hoc pairwise comparisons will use Tukey's test.

SA-6: Assess the relationship of osseous healing and implant stability at insertion across groups after 8 weeks post-extraction healing.

This SA will be addressed by including the implant stability measure as a predictor variable in the analysis of osseous healing. The statistical test that will be of primary interest for this analysis will be the two-factor interaction of stability and group.

Hypothesis III

Laser thread-textured (LTT) dental implant will preserve longitudinal peri-implant crestal bone more effectively than implants with Resorbable blast texturing (RBT).

SA-7: Assess the efficacy of LTT and RBT surface topographies when surgically implanted into extraction sockets.

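### The 52% power for SA-2 and SA-4 is omnibus power under the most favourable pattern of four means, and it is not the power of the one-to-one Group 4 contrasts planned for SA-2

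*Combined protocol and SAP*

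**What the plan says.** Section 12.5 sets a common effect size for its power figures, a medium effect, "corresponding to a difference between group means equal to 0.50 times the within-group standard deviation (sd) was calculated". It also sets a common test level: "All power estimates were based on two-sided testing at the 95% confidence level". The sample size is fixed by "assuming an effective sample size of 25 observations per extraction-implant group".

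For the aims at issue it says: "Power for SA-2, SA-4 and SA-5 was based on a one-way ANOVA model", and then "The proposed sample size would provide 52% power to detect a medium effect size". The same sentence adds that 80% power is reached at a two-group difference of 0.34 sd. No pattern for the four means is given. (SA-5 gets its own figure later, at 20 per group.)

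Section 12.4 plans the following:

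- **SA-2:** a four-group mixed-model ANOVA and post-hoc Tukey pairs. For growth-factor enrichment it plans "contrasts and F-tests to compare the mean of Group-4 with those of each of the other groups". If Groups 1-3 do not differ significantly, it adds a contrast of Group 4 with those three combined.
- **SA-4:** a four-group mixed-model ANOVA and post-hoc Tukey pairs. There are no Group 4 contrasts.

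For SA-1, by contrast, section 12.5 bases power on the planned contrast itself: "the assumed effective sample sizes of 25 and 75 would yield" about 57%.

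**The concern.** A one-way ANOVA with four groups has no single power at a 0.50 sd difference between means. Power depends on where the other two means lie, and the plan does not say. If 52% comes from the best arrangement, it is an upper limit, although the section describes its approach as conservative.

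The second issue is which test answers the question. Hypothesis II is about adding growth factors, and section 12.4 assigns that effect to Group 4 contrasts. A reader of section 12.5 would take 52% as the chance of detecting a 0.50 sd growth-factor effect. From the 0.34 sd figure the same reader would conclude that even smaller effects are detectable with 80% power. A non-significant Group 4 v Group 2 comparison could then be given more weight than it can bear.

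**Working it through.** **Inputs (section 12.5).** Four extraction groups, n = 25 effective observations each, sd = 1, difference 0.50, two-sided alpha 0.05. Section 12.5 attaches the 25 to extraction-implant groups, but the 25 and 75 used for SA-1 show that it means 25 per extraction group. Error df = 4 × 24 = 96.

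**Step 1. Reproduce the 52%.** For the overall F-test, f² = Σ(μᵢ − μ̄)²/4 and the noncentrality is λ = 25 × Σ(μᵢ − μ̄)² = 100f². Power is the probability that a noncentral F(3, 96; λ) exceeds 2.699. The four patterns below all have a largest difference of 0.50 sd:

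| Means (sd units) | Σ(μᵢ − μ̄)² | f | λ | Power |
|---|---|---|---|---|
| 0, 0, 0.50, 0.50 | 0.2500 | 0.250 | 6.25 | 51.8% |
| 0, 0, 0, 0.50 | 0.1875 | 0.217 | 4.69 | 40.0% |
| 0, 0.167, 0.333, 0.50 | 0.1389 | 0.186 | 3.47 | 30.3% |
| 0, 0.25, 0.25, 0.50 | 0.1250 | 0.177 | 3.13 | 27.5% |

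The plan's 52% is the first row. That row has the largest f possible when no two means differ by more than 0.50 sd. The plan's SA-5 figure confirms the convention: at 20 per group the two-v-two pattern gives λ = 80 × 0.25² = 5.0 and, with df 3 and 76, power 42.0%, as stated there.

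**Step 2. Group 4 v one other group (SA-2).** Noncentral t with pooled df 96: δ = 0.50/√(1/25 + 1/25) = 0.50 × √12.5 = 1.768, critical value 1.985. Power is 41.7%. Using only the two groups' own df (48) gives 41.0%. The difference detectable with 80% power is 0.80 sd.

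**Step 3. Group 4 v Groups 1-3 combined (SA-2, conditional).** δ = 0.50/√(1/25 + 1/75) = 2.165, critical value 1.985. Power is 57.3%. This agrees with the plan's own 57% for SA-1, which has the same 25 v 75 layout.

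**Step 4. One specified Tukey pair (SA-2 and SA-4).** δ = 1.768 as in step 2. The critical value is q(0.95; 4, 96)/√2 = 3.698/1.414 = 2.615. Power is 20.5% (20.4% in a simulation of 200,000 trials). The difference detectable with 80% power is 0.98 sd.

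**Step 5. The 0.34 sd.** With n = 25, the overall F-test reaches 80% power at f = 0.337. Under two-v-two, f is half the difference, so the difference is 2 × 0.337 = 0.67 sd. At a true two-v-two difference of 0.34 sd, f = 0.17 and power is 25.6%. For a given test and pattern, power cannot be 52% at 0.50 sd and 80% at 0.34 sd. The printed 0.34 matches f, not a difference.

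**The case against.** The strongest reply is that 52% is correct for the test named. Section 12.5 says openly that the figure rests on a one-way ANOVA, that ANOVA is itself a planned analysis for both aims, and leaving post-hoc pairs unpowered is common. If medium had been defined as f = 0.25, 52% would hold for any pattern with that f. The plan already concedes power far below 80%, so lower figures change no design decision.

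Most of this stands, and it limits the point in four ways.

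- A reader might infer an arithmetic error in the 52%. The documents do not support that: the number is right for the overall test under one pattern.
- A reader might infer that every Group 4 contrast has 42% power. That holds only for the three one-to-one contrasts. The combined contrast has 57%, above the stated 52%, and it is the likely route when Groups 1-3 are truly equal.
- A reader might extend the 42% to SA-4. SA-4 has no Group 4 contrasts, so only the overall and Tukey figures apply there.
- A reader might take 20% as the power of the growth-factor test, or as the chance of any Tukey finding. It is neither. Section 12.4 gives the growth-factor effect to contrasts, and the chance that at least one of the six pairs is significant is 27% to 48%, depending on the pattern.

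What does not stand is the appeal to f = 0.25, because section 12.5 defines medium as a difference between means. Nor does naming the ANOVA model settle the matter, since it does not disclose the pattern. The plan's handling of SA-1 shows that it regards the planned contrast as the right basis for power where there is one.

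**Conclusion.** The point holds as an unstated assumption and an omission. Under the plan's own definition of a medium effect and 25 effective observations per group, 52% is the upper limit of overall-test power. Other patterns with the same maximum difference give 27% to 40%. For the growth-factor effect in SA-2, each one-to-one Group 4 contrast has 42% power and the conditional combined contrast 57%. A specified Tukey pair, for SA-2 or SA-4, has 20%. None of the figures for these comparisons appears in section 12.5 under these aims. The 0.34 sd in the same sentence is a separate, plain error for about 0.67 sd.

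These results assume normal outcomes with equal variances, equal groups, unadjusted 5% contrasts, and the plan's effective sample size taken as given. The 57% also assumes that Group 4 differs by 0.50 sd from the mean of the other three groups, and it takes no account of the preliminary test that decides whether the contrast is made. That a null result would be over-read is a risk; the plan does not say how it will interpret one.

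**What to change.** In section 12.5:

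1. Label 52% as the power of the overall F-test when two groups lie at each extreme, and give 27% to 40% for the other patterns with the same 0.50 sd maximum difference.
2. For SA-2, add 42% for each one-to-one Group 4 contrast (80% power at 0.80 sd) and 57% for the conditional contrast of Group 4 with Groups 1-3 combined.
3. For SA-2 and SA-4, add 20% for a single specified Tukey pair (80% power at 0.98 sd).
4. Replace 0.34 sd by about 0.67 sd, stating that it refers to the two-v-two pattern, or else report 0.34 as f.

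The cost is a set of mostly less favourable published figures. Neither the design nor the planned analyses change.

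### Section 12.5 claims 80% power at a difference of 0.34sd in the four-group ANOVA, where power is about 26%; 80% needs about 0.67sd. SA-5's 0.72sd and the word conservative for SA-7 are also wrong.

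*Combined protocol and SAP*

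**What the plan says.** All of this is in section 12.5 (Power and Sample Size Considerations) unless noted. Testing is two-sided at the 5% level, and a medium effect is a difference of 0.50sd.

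- **SA-2 and SA-4**, one-way ANOVA on four extraction groups: "52% power to detect a medium effect size or 80% power to detect an effect size equivalent to a two-group difference of 0.34sd".
- **SA-3**, by extension: "These approximations also apply to SA-3, with the appropriate sd being the within-group standard deviation of the changes across the observation times".
- **SA-5**, histology, 20 per group: 42% power at 0.50sd, then "The effect size detectable with 80% power is equivalent to a two-group difference of 0.72sd".
- **SA-7**, infection by implant type: "The proportions in the two groups were centered on 0.50, in order to provide a conservative estimate of power", followed by "The effective sample size of 50 per group would provide 80% power to detect an odds ratio of approximately 3.2".
- **Sample size behind these figures**: "assuming an effective sample size of 25 observations per extraction-implant group". SA-1 uses 25 against 75, and the SA-7 comparison uses 50 per implant group.

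**The concern.** The SA-2/SA-4 sentence contradicts itself: one design cannot have 52% power at 0.50sd and 80% at the smaller 0.34sd. The SA-5 figure points the same way. Going from 20 to 25 observations per group cannot more than halve the detectable difference from 0.72sd to 0.34sd.

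Readers use the detectable difference to judge what a null result rules out. Taken at face value, 0.34sd suggests that a non-significant F-test for bone volume (SA-2) or bone fill (SA-4) makes differences of that size unlikely. In fact the test would miss them about three times in four. For SA-7, the most favourable placement of the proportions is presented as a safety margin.

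**Working it through.** **Inputs (section 12.5).** Four groups; two-sided 5% level; 25 effective observations per group for SA-2 and SA-4 (confirmed by 25 v 75 for SA-1); 20 per group for SA-5; 50 per implant group and an odds ratio of 3.2 for SA-7.

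**Method for the ANOVA aims.** Power = P(F′ > F crit), where F′ is noncentral F with 3 and 4n − 4 degrees of freedom and noncentrality λ = 4n·f². If two group means sit at each end of a difference d (in sd units), f = d/2. This is the most favourable pattern of means for a given d.

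**Step 1: reproduce the plan's figures.** At d = 0.50, f = 0.25.

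| Item | Stated | Recomputed |
|---|---|---|
| ANOVA, 25 per group (λ = 100 × 0.0625 = 6.25), power at 0.50sd | 52% | 51.8% |
| ANOVA, 20 per group (λ = 80 × 0.0625 = 5.00), power at 0.50sd | 42% | 42.0% |
| SA-1, t-test 25 v 75 | 57%; 0.65sd | 57.3%; 0.653sd |
| SA-8 and SA-9, t-test 50 v 50 | 70%; 0.565sd | 69.7%; 0.566sd |

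The plan's own 52% and 42% therefore fix the conversion d = 2f. The t-test rows, including "80% power to detect a difference of 0.565sd between the groups", confirm 25 per extraction group and 50 per implant group.

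**Step 2: the 0.34sd claim.** At d = 0.34, f = 0.17 and λ = 100 × 0.0289 = 2.89, so power is 25.6%. Reaching 80% at that difference would take 96 per group. With 25 per group, 80% power needs f = 0.337:

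- two means at each extreme: d = 2 × 0.337 = 0.674sd;
- only one group differing: d = 4 × 0.337/√3 = 0.778sd (power at 0.34sd is then 19.9%).

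The value 0.337 rounds to the printed 0.34.

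**Step 3: SA-5.** With 20 per group, 80% power needs f = 0.379, so d = 2 × 0.379 = 0.758sd. Power is 75.4% at 0.72sd and 80.3% at 0.76sd. As a cross-check on step 2, moving from 20 to 25 per group should multiply the detectable difference by 0.674/0.758 = 0.89; the printed figures give 0.34/0.72 = 0.47.

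**Step 4: SA-2's growth-factor contrast.** Section 12.4 will "compare the mean of Group-4 with those of each of the other groups". For 25 v 25 with 96 error degrees of freedom, unadjusted, 80% power needs 0.80sd. The 0.67sd figure must therefore be labelled as belonging to the overall F-test.

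**Step 5: SA-7.** Pooled two-proportion test, 50 per group, odds ratio fixed at 3.2, proportions placed symmetrically about a centre. The documents give no infection rate, so every centre other than 0.50 is an assumption.

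| Centre | Proportions | Power |
|---|---|---|
| 0.50 | 35.9% v 64.1% | 81.7% |
| 0.40 | 26.5% v 53.5% | 79.8% |
| 0.30 | 18.3% v 41.7% | 73.2% |
| 0.20 | 11.2% v 28.8% | 59.6% |
| 0.10 | 5.2% v 14.8% | 36.2% |

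The odds ratio of about 3.2 is sound at centre 0.50 (exactly 80% power at 3.12). Moving the centre away from 0.50 only lowers power.

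**Step 6: minor slips.** The total of 160 observations, given for an average of 3 extractions, is 80 × 2. With VIF = 1 + (m − 1) × 0.5, m = 1.5 gives 1.25 and 120/1.25 = 96; m = 2 gives 1.5 and 160/1.5 = 106.7, or 26.7 per group. An average of 3 would give 240, 2.0, 120 and 30. The worked VIFs thus subtract 1 from the cluster size, although the printed formula does not; that may be a loss in text conversion. None of these slips changes a later power figure.

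**The case against.** The best case for leaving this alone is that little depends on it. The correct 52% stands in the same sentence, so a careful reader can see the error, and no analysis rule or enrolment number uses 0.34sd. That is right and it limits the severity, but the figure is still a false statement in the sample-size justification.

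Other points, and what stands of each:

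- **SA-3.** Its primary test is the group-by-time interaction, not the four-group overall F-test. This stands to the extent that 26% is not a computed power for SA-3. But the plan itself carries the approximation over to SA-3, so the wrong figure goes with it.
- **SA-5.** The gap between 0.72 and 0.758sd is about 5%. It is small, but a chi-square approximation gives 0.738sd, so that shortcut does not explain it.
- **SA-7.** Centring on 0.50 is conservative for a fixed risk difference: at a difference of 0.283, power is 81.8% at centre 0.50 and 95.4% at 0.20. True, but the plan states the effect as an odds ratio, where the direction reverses. The size of the loss depends on the unknown infection rate; the direction does not. The two-proportion test is also only a stand-in for the planned Cox model.
- **The assumed 25 per group.** The plan's own case of 1.5 sites per participant gives 24, where power at 0.50sd is 49.9% and the detectable difference 0.69sd. The corrected figures are conditional on 25, as the plan's are.

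**Conclusion.** The concern holds. Given 25 effective observations per group and the overall F-test, the claimed 80% power at 0.34sd is really 25.6%. The true detectable difference is 0.67sd under the most favourable pattern of means and 0.78sd if only one group differs, so the plan overstates its sensitivity by a factor of about two. That f was reported as a difference is an inference, though a strong one; that the figure is wrong does not depend on it.

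The SA-5 error is small (0.72 for 0.76sd, about 5 points of power). In SA-7 the odds ratio is right and only the claim of conservatism is wrong. The power figures at 0.50sd (57%, 52%, 42%) are correct on the plan's assumptions and openly disclosed. This should be corrected, but the damage is confined to the stated justification.

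**What to change.** Change the text of section 12.5 only.

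1. **SA-2 and SA-4.** Keep the sentence naming the one-way ANOVA model. Replace the next one with, for example: *With 25 effective observations per group (SA-2 and SA-4; SA-5 is given below), the overall F-test has 52% power for a medium effect and 80% power for f = 0.34, which corresponds to a two-group difference of about 0.67sd under the most favourable pattern of means, or about 0.78sd if only one group differs.* Leave the SA-3 sentence and its definition of the sd as they are.
2. **SA-5.** Replace 0.72sd with 0.76sd.
3. **SA-7.** Keep the odds ratio of about 3.2 with proportions centred on 0.50. Delete the claim that this is conservative, and add that for a fixed odds ratio power is highest at this centre and falls as infection becomes less common.
4. **Minor slips.** Change the average of 3 extractions to 2; give the VIF as 1 + (average cluster size − 1) × ICC; and describe the effective sample size as 25 per extraction group and 50 per implant group.

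The cost is a text correction and less favourable stated detectable differences. Enrolment and analysis do not change.

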This SA will be addressed using a survival analysis approach. The primary outcome measure will be presence of signs and symptoms of infection at the implant site, since implant failure is expected to be rare to non-existent. Frequencies of occurrence of infection will be tabulated for each implant type.

Cox proportional hazards regression will be used to evaluate the rates of infection for LTT and RBT implants, allowing for adjustment for potential confounding variables and covariates. A blocking variable representing the individual subject will be included in order to reflect multiple implants per study subject.

SA-8: Assess peri-implant soft tissue healing adjacent to LTT and RBT surfaced implants

The JEMPT index will be evaluated at the time of final restoration and at 12 and 24 months follow-up evaluations. Mixed model ANOVA will be used to compare changes over time between implant types. The statistical test that will be of primary interest is the implant type by time interaction.

SA-9: Assess changes in the longitudinal crestal bone levels across extraction groups and between implant groups at 12 and 24 months after surgical placement.

The analysis for the SA will be mixed-model ANOVA, accounting for multiple observations per subject. The statistical test that will be of primary interest is the F-test for surface type by time interaction.

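### Section 12.5 calls centring the SA-7 infection proportions on 0.50 conservative, but for a fixed odds ratio that centre gives the highest power, so the stated 80% is a best case

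*Combined protocol and SAP*

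**What the plan says.** Section 12.4, under SA-7, makes infection the outcome for comparing the two collar surfaces: "The primary outcome measure will be presence of signs and symptoms of infection at the implant site, since implant failure is expected to be rare". The analysis is a survival model: "Cox proportional hazards regression will be used to evaluate the rates of infection for LTT and RBT implants".

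Section 12.5 bases the power on a simpler test: "Power for comparison of rates of infection signs for SA-7 was based on the chi-square test for the odds ratio". It then gives the assumption at issue, "The proportions in the two groups were centered on 0.50, in order to provide a conservative estimate of power", and the result, "The effective sample size of 50 per group would provide 80% power to detect an odds ratio of approximately 3.2". The significance level comes from the same section: "All power estimates were based on two-sided testing at the 95% confidence level".

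Neither section gives an expected infection rate, or power at any other rate.

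**The concern.** Whether 0.50 is a cautious centre depends on the scale of the effect. If the difference between two proportions is held fixed, binomial variance peaks at 0.50, so that centre gives the lowest power. If the odds ratio is held fixed, the difference between the proportions shrinks as they move towards 0 or 1. The information on the log odds ratio falls with it, so 0.50 gives the highest power. Section 12.5 states its effect as an odds ratio but uses the justification that belongs to a risk difference.

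What is at stake is how the figure is read. A reader told that 80% is conservative will take it as a floor, when it is close to a ceiling. This is the only power statement in the plan for an infection comparison, and infection is the declared primary outcome for SA-7.

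**Working it through.** **Inputs from the documents (section 12.5).** Two-sided 5% level, chi-square test of two proportions, n = 50 effective observations per implant group (taken as given), odds ratio (OR) 3.2, proportions centred on 0.50.

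**Assumed input.** The infection rate, which the documents do not give. It is varied below. The reference arm is the arm with the lower rate.

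**Formula.** With d = p2 − p1 and p̄ the mean of p1 and p2,

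power = Φ{ [d√n − 1.96√(2p̄(1−p̄))] / √(p1(1−p1) + p2(1−p2)) }.

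**Step 1: reproduce the plan's figure.** Centring on 0.50 with OR 3.2 gives p1 = 1/(1+√3.2) = 0.359 and p2 = √3.2/(1+√3.2) = 0.641, so d = 0.283.

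- d√50 = 2.000
- 1.96√0.50 = 1.386
- √(0.230 + 0.230) = 0.678
- Power = Φ(0.614/0.678) = Φ(0.906) = 0.817

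For 80% power, 48 per group suffice, and the smallest OR detectable with 50 per group is 3.12. Exact enumeration gives 83% for the chi-square test and 78% for Fisher's test. The plan's number is sound at its own inputs.

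**Step 2: hold the OR at 3.2 and move the rate.** For a reference rate p1, p2 = 3.2·p1/(1−p1) ÷ [1 + 3.2·p1/(1−p1)]. Example at 10%: p2 = 0.3556/1.3556 = 0.262, d√50 = 1.148, 1.96√(2 × 0.181 × 0.819) = 1.068, denominator √(0.090 + 0.1935) = 0.532, so power = Φ(0.150) = 0.56.

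| Reference-arm rate (assumed) | Other arm at OR 3.2 | Power for OR 3.2 | OR detectable with 80% power |
|---|---|---|---|
| 5% | 14.4% | 35% | 6.2 |
| 10% | 26.2% | 56% | 4.4 |
| 20% | 44.4% | 75% | 3.4 |
| 25% | 51.6% | 79% | 3.2 |
| 35.9% (the plan's case) | 64.1% | 82% | 3.1 |
| 50% | 76.2% | 78% | 3.3 |

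A scan of reference rates from 1% to 90% puts the maximum at 0.359, which is the plan's case.

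Indexed by the average of the two rates, power for OR 3.2 is 82% at 50%, 80% at 40%, 73% at 30%, 60% at 20% and 36% at 10%. The two listings agree and differ only in how the rate is defined: an average of 10%, for example, means 5.2% against 14.8%.

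**Step 3: why the direction reverses.** The large-sample variance of the log OR is 1/[n·p1(1−p1)] + 1/[n·p2(1−p2)].

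- Plan's case: 2/(50 × 0.230) = 0.174, standard error 0.417, and ln 3.2 = 1.163 is 2.79 standard errors.
- 10% reference rate: 1/(50 × 0.090) + 1/(50 × 0.1935) = 0.222 + 0.103 = 0.326, standard error 0.571, and the same log OR is 2.04 standard errors.

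With the 28.3-point risk difference held fixed instead, power is 82% at centre 0.50 and 95% at centre 0.20. On that scale 0.50 would be conservative.

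**Step 4: the planned Cox model.** It depends on the rate in the same way, because its information comes from the number of events. As a guide, a hazard ratio of 3.2 (not the same quantity as an OR of 3.2) needs about 4(1.96 + 0.84)²/(ln 3.2)² = 31.4/1.353, or 24 events after rounding up. The 0.50-centred case implies about 50 events in 100 effective observations. A pooled rate of 10% implies about 10.

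**The case against.** The best defence is that nothing is miscalculated. The plan discloses its centring, its figure reproduces at the stated inputs, and for a risk difference the label would be correct. All of that stands. The defect is a misapplied justification and what it implies about the figure, not a wrong number.

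The second defence is that no low infection rate is established, and that also stands. The phrase in section 12.4 about rarity concerns implant failure, and it is the reason given for using infection signs instead. The peri-operative antibiotics in sections 5.3 and 5.7 do not bound a rate observed up to 24 months. Section 10.2 lists suppuration and erythema among the signs to be examined, and smokers are enrolled. With a reference-arm rate of about 30% to 40% there is no shortfall, and at 20% to 25% it is small.

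Three stronger readings are therefore not supported:

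- A reader might infer that the trial cannot detect an odds ratio of 3.2. The calculations show only that power is below 80% at lower rates, and those rates are assumed.
- A reader might infer that the trial would miss such an effect more often than find it. That holds only at average rates of about 15% or below (power 49% at 15%), or a reference-arm rate of about 8%.
- A reader might infer that a null result would be presented as evidence of equal safety. The plan makes no such claim. SA-7 is an efficacy aim, and section 12.3 evaluates safety separately.

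The choice of index also matters. At an average rate of 10% the detectable odds ratio is about 13, but that implies under one expected event among 50 in the lower-rate arm, where the approximation is unreliable. At a reference-arm rate of 10% it is 4.4.

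**Conclusion.** Wrong as written, and a wording correction more than a threat to the trial. Calling the 0.50 centre conservative is backwards for an effect stated as an odds ratio, whatever the true infection rate. The 80% power for an odds ratio of 3.2 is a best case.

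How much this matters depends on an infection rate that the documents do not supply. The loss is slight at reference-arm rates of 20% to 25% and substantial at 10% or below. These results assume 50 effective independent observations per group, equal allocation and the two-sided 5% chi-square test, all as in section 12.5. The t-test power for bone height, also listed under SA-7, is unaffected.

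**What to change.** In section 12.5:

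1. Delete the clause that gives conservatism as the reason for centring on 0.50.
2. Label the odds ratio of 3.2 as the most favourable case, with infection in about 36% of one group and 64% of the other.
3. Add power for an odds ratio of 3.2, or the odds ratio detectable with 80% power, at reference-arm infection rates of 5%, 10% and 20%. With 50 effective observations per group these are 35%, 56% and 75%, or 6.2, 4.4 and 3.4. Say explicitly that the rate is that of the lower-rate arm and not the average of the two.

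If the investigators have an expected infection rate, they should state it with its source.

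The cost is a few sentences. Sample size, outcome, analysis and conduct stay as they are. The only drawback is a less favourable stated power.
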